11.4 Analysis of Vital Signs and Weight

11.4.1 Variables and Criteria Defining Abnormality

The following vital sign parameters will be assessed: Systolic blood pressure [mmHg], Diastolic blood pressure [mmHg], Pulse [beats per minute], Respiratory rate [breaths per minute], Temperature [$^{\circ}\text{C}$], Weight [kg]. The following table presents the Criteria for Potentially Clinically Important Vital Sign Findings. Of note, a post baseline value must

be more extreme than the baseline value to be considered a potentially clinically important finding.

Table 15. Criteria for Potentially Clinically Important Vital Sign Findings

Vital Sign	Category	Criteria for Potential Clinically Important Vital Signs
Systolic Blood Pressure	Low Value	≤ 90 mmHg and decrease ≥ 20 mmHg from Baseline
	High Value	≥ 160 mmHg and increase ≥ 20 mmHg from Baseline
Diastolic Blood Pressure	Low Value	≤ 50 mmHg and decrease ≥ 15 mmHg from Baseline
	High Value	≥ 105 mmHg and increase ≥ 15 mmHg from Baseline
Pulse	Low Value	≤ 50 bpm and decrease ≥ 15 bpm from Baseline
	High Value	≥ 120 bpm and increase ≥ 15 bpm from Baseline

11.4.2 Statistical Methods

Changes from Baseline to each visit and to the final value in vital sign parameters will be summarized with the mean, standard deviation and median. The Baseline and final value means will also be presented for subjects who have both the Baseline and final values (see Section 6.0 for the definition of Baseline and final values).

For baseline, if there are multiple measurements on the same day, the last measurement prior to the first dose of study drug will be used as the Baseline vital sign value. If there are multiple post-baseline measurements on the same day, average value will be used.

For systolic blood pressure, diastolic blood pressure and pulse, a listing of all subjects with any vital sign value meeting criteria for potentially clinically important values will be provided. For each of these subjects, the whole course of the respective parameter will be listed. The number and percentage of subjects who have at least one value meeting criteria for potentially clinically important values will be provided for each selected vital sign parameter.

All analyses will be conducted in the Safety Population. Table for potentially clinically important vital signs will also be summarized in the ALL_RZB Population.

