5.3.2 Vital Signs

Vital signs evaluations will be performed at visits as shown in the Flow Chart. This includes systolic/diastolic blood pressure, pulse rate, temperature, and respiratory rate. Blood pressure, pulse rate, and respiratory rate will be measured after patients have been sitting comfortably for at least five minutes. Measurement of vital signs should precede blood sampling to avoid the impact of blood sampling on the vital measurements. At dosing visits vital signs

evaluations will be performed pre-dose and at Visit 2 and Visit 3 additional evaluations will be taken at approximately 5 minutes post-dose (5 minutes after last injection) and approximately 60 minutes post-dose (60 minutes after last injection).

Patients should be closely monitored for signs and symptoms of hypersensitivity reactions for approximately 2 hours after the last injection at Visit 2 and for approximately 1 hour after the last injection at all other visits with drug administration. Hypersensitivity reactions should be treated according to medical standards. Pre-medications for further injections might be considered and will be agreed on between investigator and BI clinical monitor.

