ITT/Safety (Part A)	RZB_75	Subjects who randomized to risankizumab 75 mg.
	RZB_150	Subjects who randomized to risankizumab 150 mg.
	PBO	Subjects who randomized to either of the two placebo arms.
ITT/Safety (Part B)	RZB_75/RZB_75	Subjects who randomized to risankizumab 75 mg.
	RZB_150/RZB_150	Subjects who randomized to risankizumab 150 mg.
	PBO/RZB_75	Subjects who randomized to placebo and then risankizumab 75 mg entered Part B
	PBO/RZB_150	Subjects who randomized to placebo and then risankizumab 150 mg entered Part B
ITT/Safety (entire study)	RZB_75/RZB_75	Subjects who randomized to risankizumab 75 mg.
	RZB_150/RZB_150	Subjects who randomized to risankizumab 150 mg.
ALL_RZB	ALL_RZB	Subjects who received at least one dose of risankizumab 75/150 mg.

5.2**Variables Used for Stratification of Randomization**

Randomization will be stratified by concomitant PsA at baseline (Yes versus No) and body weight (≤ 90 kg versus > 90 kg).

6.0**Analysis Conventions****Definition of Baseline**

The last non-missing observation collected on or before the date of the first dose of study drug injection will be used as Baseline for summary of demographics and disease characteristics, safety and efficacy analyses, with the exception that:

- The last evaluation on or prior to the date of first dose of risankizumab will be used for the safety analyses in Part B among subjects randomized to placebo at Week 0, and the safety analyses in the ALL_RZB Population.
- For all vital sign assessments, only assessments prior to first dose time will be considered, since vital signs are to be assessed both pre- and post-dose in some visits.

Entry of Part B is defined as the last non-missing observation collected on or before the date of the first dose of study drug in Part B for PBO/RZB_75 and PBO/RZB_150 arms and last non-missing observation collected on or before the date of Week 16 visit for RZB_75/RZB_75 and RZB_150/RZB_150 arms.

Definition of Final Observation (Applicable to Safety Analyses)

Final observation in Part A is defined as the last non-missing observation collected within 105 days following the last dose of study drug in Part A for those who do not enter Part B, and on or before the first dose date of study drug injection in Part B for subjects who entered Part B. For vital sign assessments, only assessments prior to the first dose of study drug injection in Part B will be included in the analysis for Part A.

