Final observation for Part B is defined as the last non-missing observation collected within 105 days following the last dose in Part B.

Final observation for the entire study analyses is defined as the last non-missing observation collected within 105 days following the last dose of study drug.

Final observation for ALL_RZB Population is defined as the last non-missing observation collected within 105 days following the last dose of risankizumab.

Definition of Rx Days in Each Period (Days Relative to the Date of First Dose of Study Drug in Each Period)

Rx Days are calculated for each time point relative to the date of first dose of study drug. They are defined as the number of days between the day of the first dose of study drug and the specific time point. Rx Days are negative values when the time point of interest is prior to the first study drug dose day. Rx Days are positive values when the time point of interest is on or after the first study drug dose day. The day of the first dose of study drug is defined as Rx Day 1, while the day prior to the first study drug dose is defined as Rx Day –1 (there is no Rx Day 0).

Rx Days for Part A and entire study will be defined relative to the date of first dose of study drug. Rx days for Part B will be defined relative to the date of the date of the first study drug injection on or after Week 16.

Definition of Analysis Windows

All time points and corresponding time windows are defined based on Rx Days. The visit schedule with accompanying details can be found in Flow Chart and Section 6.1 of the protocol.

For efficacy analyses, local tolerability, ECG, laboratory parameters, and vital sign variables, analysis windows are constructed using the following algorithm:

- Determine the nominal Rx day for each visit (e.g., Week 4 [4 weeks after Baseline visit] equals Rx Day 29).
- In order to include all post baseline data, the first post-baseline interval starts on the first day after the first dose of study drug (Rx Day 2).

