- Determine the window around a specific nominal Rx day by adding or subtracting half of the interval between adjacent visits (e.g., days between Week 4 and Week 8 is 28). The threshold between adjacent visits is determined by splitting the interval evenly between the visits. If the resulting split is between Rx days, then the threshold is determined as the midpoint between the adjacent visits. If the resulting split is on an Rx day, then the threshold is determined as being between that Rx day and the Rx day prior to it (e.g., the split between Week 4 and Week 8 would be between Rx Days 43 and 44).
- If more than one assessment is included in a time window the assessment closest to the nominal day will be used. If there are two observations equidistant to the nominal day, the later one will be used in analyses. If more than one assessment is included on the same day, then the worst assessment on that day will be used in analyses, except those specified in Section 11.0.

The following analysis windows have been specified for the analysis of efficacy, laboratory parameters, and vital signs, etc. for each analysis period. In order to include all post baseline data, the first post baseline interval starts on the day after the date of first study drug injection in each period (Rx Day 2) for all efficacy variables.

For subjects who were randomized and not dosed date of randomization will be used for determining window definitions.

Table 2.
Visit Windows for Analysis of PASI, Vital Signs, and Local Tolerability in Part A (ITT/PP/Safety Populations)

Window Label	Target Day	Interval
Baseline	1	$\leq 1^a$
Week 4	29	[2, 43]
Week 8	57	[44, 71]
Week 12	85	[72, 99]
Week 16	113	[100, 127 ^b]

Rx Day calculated relative to first dose date of study drug. For subjects randomized but not dosed, Rx Day calculated relative to Randomization.

- a. There is no baseline for local tolerability measurements. If time is collected in vital signs, restrict to records prior to the first dose of study drug.
- b. The minimum of upper bound and the day of the first dose date in Part B (and within 105 days of last dose for safety analyses).

Table 3.
Visit Windows for Analysis of Safety Laboratory Tests in Part A (Safety Population)

Window Label	Target Day	Interval
Baseline	1	≤ 1
Week 8	57	[2, 85]
Week 16	113	[86, 141*]

Rx Day calculated relative to first dose date of study drug.

* The minimum of upper bound, the day of the first dose date in Part B, and 105 days of last dose.

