Table 4.
Visit Windows for Analysis of ECG in Part A (Safety Population)

Window Label	Target Day	Interval
Baseline	1	≤ 1
Week 4	29	[2, 71]
Week 16	113	[72, 155*]

Rx Day calculated relative to first dose date of study drug.

* The minimum of upper bound, the first dose date in Part B, and the last dose + 105 days.

Table 5. Visit Windows for Analysis of sPGA, PSS, DLQI, HAQ-DI, Pain VAS, Investigator's Global Assessment VAS, Patient's Global Assessment VAS, CRP as an ACR 20 Component, SJC, and TJC in Part A (ITT Population)

Window Label	Target Day	Interval
Baseline	1	≤ 1
Week 16	113	[2, 225*]

Rx Day calculated relative to first dose date of study drug. For subjects randomized but not dosed, Rx Day calculated relative to Randomization.

* The minimum of upper bound and the day of the first dose date in Part B.

Table 6. Visit Windows for Analysis of PASI, Vital Signs, and Local Tolerability in Part B (ITT/Safety Population)

Window Label	Target Day	Interval
Entry of Part B	1	$\leq 1^a$
Week 22	43	[2, 64]
Week 28	85	[65, 106]
Week 34	127	[107, 148]
Week 40	169	[149, 190]
Week 46	211	[191, 232]
Week 52	253	[233, 267]
Week 56	281	[268, 295 ^b]

Rx Day calculated relative to the first dose date on or after Week 16 for PBO/RZB_75 and PBO/RZB_150 arms, and relative to the date of Week 16 visit for RZB_75/RZB_75 and RZB_150/RZB_150 arms. PASI only evaluated from Week 22 to 52. Local tolerability only evaluated from Week 22 to 40.

a. If time is collected for vital sign, restrict to records prior to the first dose of study drug in Part B.

b. The minimum of upper bound and 105 days after the last dose.

Subjects who enter the Open Label Extension Study 1311.31 will not have Week 56 evaluations.

Table 7. Visit Windows for Analysis of sPGA, PSS, DLQI, HAQ-DI, Pain VAS, Investigator's Global Assessment VAS, Patient's Global Assessment VAS, SJC, TJC, Laboratory Tests, and ECG in Part B (ITT/Safety Population)

Window Label	Target Day	Interval
Entry of Part B	1	≤ 1
Week 28	85	[2, 127]
Week 40	169	[128, 211]
Week 52	253	[212, 294 ^a]

Rx Day calculated relative to the first dose date on or after Week 16 for PBO/RZB_75 and PBO/RZB_150 arms, and relative to the date of Week 16 visit for RZB_75/RZB_75 and RZB_150/RZB_150 arms.

a. The minimum of upper bound and 105 days after the last dose.

Table 8. Visit Windows for Summary of Study Drug Injections in Part A

Window Label	Target Day	Time Window
Week 0	1	≤ 1
Week 4	29	[2, 57 ^a]

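### The by-visit vital-sign summaries omit the Day 1 post-dose readings and dilute the Week 4 ones; whether the clinically-important outputs use single or averaged values is not stated

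*SAP*

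**What the plan says.** Protocol 5.3.2 requires vital signs before dosing at every dosing visit and, in addition, "at Visit 2 and Visit 3 additional evaluations will be taken at approximately 5 minutes post-dose" and again at about 60 minutes. Note 4 to the Flow Chart says the same. Visit 2 is Day 1 and Visit 3 is Week 4.

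SAP Section 6.0 restricts the baseline: "For all vital sign assessments, only assessments prior to first dose time will be considered". Note a to Table 2 repeats this with a condition: "If time is collected in vital signs, restrict to records prior to the first dose of study drug". The windows then begin the next day: "In order to include all post baseline data, the first post-baseline interval starts on the first day after the first dose of study drug". Table 2 sets Week 4 at Rx Days 2 to 43.

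For several readings on one day, Section 6.0 takes the worst, except where Section 11.0 specifies otherwise. Section 11.4.2 does so for vital signs: "If there are multiple post-baseline measurements on the same day, average value will be used". It then plans change from baseline to each visit and to the final value. For systolic pressure, diastolic pressure and pulse, it also plans a listing of subjects with any value meeting Table 15, showing the full course of that parameter, and a count of subjects with at least one such value.

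In Part B, Table 6 gives Week 56 a target of Day 281 and an interval of 268 to 295, with this limit on the upper end: "The minimum of upper bound and 105 days after the last dose".

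**The concern.** The 5- and 60-minute readings add to the visit schedule only the ability to see a change shortly after injection. A by-visit table that leaves out the first-dose readings and blends the second-dose readings with the pre-dose value does not report that change. The omission also defeats the stated aim of the window rule, which is to include all post-baseline data.

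All four scheduled post-dose readings fall in Part A, the period with a concurrent placebo group. Protocol 7.3.4 says that vital signs during the trial will be assessed for changes from before treatment. At stake is how fully the planned tables describe acute changes by arm, above all changes too small to meet Table 15 and changes in temperature or respiratory rate.

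The averaging also affects the Week 4 visit mean. Week 4 becomes a mixture of pre- and post-dose values, while the other post-baseline Part A visits have no scheduled post-dose reading.

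**Working it through.** The plan gives no figure to reproduce here. The check applies its rules to the scheduled readings.

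**Step 1: assign each reading to a window** (schedule from Protocol 5.3.2; windows from SAP Section 6.0, Table 2).

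| Reading | Rx Day | Window |
|---|---|---|
| Visit 2 pre-dose | 1 | Baseline |
| Visit 2, 5 minutes | 1 | none |
| Visit 2, 60 minutes | 1 | none |
| Visit 3 pre-dose | 29 | Week 4 |
| Visit 3, 5 minutes | 29 | Week 4 |
| Visit 3, 60 minutes | 29 | Week 4 |

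Two of the four post-dose readings are in no window. They could enter the final-value summary only for a patient with no later reading.

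**Step 2: apply the same-day average at Week 4.** The Visit 3 pre-dose reading is itself post-baseline, so it is averaged too. Let D5 and D60 be the changes from the same-day pre-dose value:

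average = (pre + (pre + D5) + (pre + D60)) / 3 = pre + (D5 + D60) / 3.

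A change D at one time contributes D/3; the same change at both times contributes 2D/3.

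**Step 3: see what this does to Table 15, if averages feed it.** The low systolic criterion is 90 mmHg or less and a fall of at least 20 mmHg from baseline. The documents give no typical values, so assume 120 mmHg at baseline and at Visit 3 pre-dose.

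| D5, D60 (mmHg) | Average | Change | Met by a single value? | Met by the average? |
|---|---|---|---|---|
| -30, 0 | 110 | -10 | yes | no |
| -30, -30 | 100 | -20 | yes | no |
| -60, 0 | 100 | -20 | yes | no |
| -45, -45 | 90 | -30 | yes | yes |

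On averages, D5 + D60 must reach 3 × (90 - 120) = -90 mmHg: a fall of 90 at one time, or 45 at both. The same happens from a lower start: with 110 at baseline and pre-dose, 85 at 5 minutes and 105 at 60 minutes, the average is (110 + 85 + 105) / 3 = 100. The reading of 85 meets the criterion and the average does not.

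**Step 4: the Week 56 row.** With Week 16 on Day 113, Part B day = study day - 112.

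- Week 40 dose: Day 281 - 112 = 169. Cap: 169 + 105 = 274, before the target of 281.
- Week 56 visit: Day 393 - 112 = 281, with ±7 days giving 274 to 288, which is 15 days.
- Overlap of 268 to 274 with 274 to 288: 1 of 15 days.
- The Week 40 dose may itself fall 7 days either side, on Part B Day 162 to 176. The cap then runs from 267 to 281, and the overlap from 0 to 8 of 15 days.

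**The case against.** The strongest reply is that the plan has another route to these readings. The listing in Section 11.4.2 is triggered by any qualifying value and the count by at least one; neither is tied to a visit window. Section 11.1 compares risankizumab with placebo pairwise in the Safety Population. The laboratory section sets its same-day rule output by output (average for means, last value for shifts, worst value for clinically important and graded values). The averaging sentence for vital signs may likewise be meant only for the means, leaving the worst-value default of Section 6.0 for Table 15.

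Clinical routes exist too. Patients are watched for hypersensitivity for about 2 hours after dosing at Visit 2 and about 1 hour at the other dosing visits. Vital-sign changes judged clinically relevant are recorded as adverse events, and hypersensitivity and anaphylactic reaction are Areas of Safety Interest.

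Much of this stands. A reader might infer that the plan cannot show an acute post-injection change at all, or that the comparison with placebo is lost. The documents do not support either reading, for the reasons just given. What the reply leaves open is narrower. The averaging sentence has no stated scope and comes directly before the clinically-important outputs, and vital signs lack the separate worst-value sentence that laboratory data have. The SAP also does not say that Day 1 post-dose values count for Table 15. Table 15 does not cover temperature or respiratory rate.

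A reader might also see a contradiction in the lack of post-dose readings at Visit 6, when placebo patients first receive active drug. There is none: the Flow Chart note and Protocol 5.3.2 agree on Visits 2 and 3, and the dosing table says nothing different.

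On Week 56, the 105-day limit is the protocol's 15-week residual effect period, used consistently elsewhere in the SAP. Simply removing it would mix post-treatment with on-treatment data.

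**Conclusion.** The point holds for the by-visit change summaries. Two of the four scheduled post-dose readings are omitted, and at Week 4 a change at one post-dose time appears at one third of its size (two thirds if it is equal at both times). For systolic and diastolic pressure and pulse, readings that cross a Table 15 threshold should appear if single values are used; on averages, some would be missed. Changes below the thresholds, and all changes in temperature and respiratory rate, are omitted or diluted in the planned vital-sign summaries. This weakens the description of safety; it does not touch the efficacy analyses.

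The window assignment and the one-third factor follow from the rules alone. The blood-pressure examples rest on assumed values.

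The Week 56 row is a separate, smaller defect. It keeps 1 of 15 permitted visit days with on-schedule Week 40 dosing, and 0 to 8 over the dosing window. The protocol places this follow-up 16 weeks (112 days) after the last dose, beyond the 105-day limit, so the row will be largely empty. Patients entering the extension have no Week 56 evaluation in any case.

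**What to change.** In SAP 11.4.2:

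1. Use the pre-dose value alone for the Week 4 visit mean.
2. Add one descriptive table by arm of the change from the same-day pre-dose value to 5 and to 60 minutes, at Visits 2 and 3, for all vital signs measured at those times.
3. State that Table 15 is applied to each single post-baseline reading, including those taken after dosing on Day 1, and that the same-day average does not apply to the listing or the count.

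In SAP Table 6, delete the Week 56 row, or keep the 105-day limit for on-treatment summaries and report the Week 56 readings separately as post-treatment.

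The cost is SAP wording and one extra table. The readings are already scheduled, so no new data collection is needed, provided the database identifies each reading as pre-dose, 5-minute or 60-minute. Table 2 makes its baseline restriction conditional on time being collected, so this should be confirmed.

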5.3.6.2 Adverse event collection and reporting

AE Collection

[figure not shown]
The Investigator shall maintain and keep detailed records of all AEs in their patient files. The following must be collected and documented on the appropriate CRF by the investigator:

- From signing the informed consent onwards through the residual effect period (REP) until individual patient's end of trial:
 - all AEs (serious and non-serious) and all AESIs.

However, if an individual patient discontinues trial medication prematurely but stays in the trial (i.e., if further visits including telephone visits, or vital status assessments are planned) from then on and until the individual patient's end of the trial the investigator must report related SAEs and related AESIs

- After the individual patient's end of trial:

The investigator does not need to actively monitor the patient for AEs but should only report relevant SAEs and relevant AESIs of which the investigator may become aware of.

The REP is defined as 15 weeks after the last trial medication application. All AEs which occurred through the treatment phase and throughout the REP will be considered as on treatment please see [Section 7.3.4](#). Events which occurred after the REP will be considered as post treatment events.

AE reporting to sponsor and timelines

The investigator must report SAEs, AESIs, and non-serious AEs which are relevant for the reported SAE or AESI, on the BI SAE form via fax immediately (within 24 hours) to the sponsor's unique entry point (country specific contact details will be provided in the ISF). The same timeline applies if follow-up information becomes available. In specific occasions the investigator could inform the sponsor upfront via telephone. This does not replace the requirement to complete and fax the BI SAE form.

All SAEs and AESIs must be reported immediately to the head of the trial site.

With receipt of any further information to these events, a follow-up SAE form has to be provided. For follow-up information the same rules and timeline apply as for initial information.

Information required

For each AE, the Investigator should provide the information requested on the appropriate CRF pages and the BI SAE form. The Investigator should determine the causal relationship to the trial medication.

The following should also be recorded as an (S)AE in the eCRF and SAE form (if applicable):

- Worsening of the underlying disease or of other pre-existing conditions

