11.3 Analysis of Laboratory Data

For the assessments of laboratory data, values observed more than 105 days after the last dose of study drug will be excluded.

Listing and descriptive statistics of laboratory values over time, change from baseline, and extreme abnormal value on treatment will be provided. Extreme abnormal value is the value which is most significantly away from the reference range. Frequency of subjects with transitions relative to reference range and listing of subjects with significant abnormal laboratory values will be presented as well.

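### In Part B, by-visit vital-sign and ECG summaries (except the last row of each), the any-value vital-sign count and the maximum-QTc categories lack the 105-day post-dose limit applied to laboratory data

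*SAP*

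**What the plan says.** Protocol 5.3.6.2 sets the residual effect period for adverse events: "The REP is defined as 15 weeks after the last trial medication application". It adds: "Events which occurred after the REP will be considered as post treatment events". SAP 11.2.1 applies this to treatment-emergent events as 105 days.

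For laboratory data, SAP 11.3 has a general rule: "For the assessments of laboratory data, values observed more than 105 days after the last dose of study drug will be excluded". SAP 11.4 (vital signs) and 11.5 (ECG) have no equivalent sentence.

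For vital signs and ECG the limit appears in two other places, both in SAP 6.0:

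- **Final observation.** The definitions for safety analyses stop at 105 days after the last dose for Part B, the entire study, ALL_RZB, and Part A patients who do not enter Part B.
- **Visit windows.** In Part A the Week 16 rows are capped. Table 2 note b (vital signs) reads "and within 105 days of last dose for safety analyses", and the note to Table 4 (ECG) has the same limit. In Part B the note "The minimum of upper bound and 105 days after the last dose" is attached to one row per table: Week 56 in Table 6 (vital signs) and Week 52 in Table 7 (ECG and laboratory tests).

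SAP 11.4.2 counts the "number and percentage of subjects who have at least one value meeting criteria for potentially clinically important values" and repeats that table in ALL_RZB. SAP 11.5 classifies each patient by maximum QTcF and QTcB and by maximum change, in the Safety Population only. Neither section limits these to 105 days.

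Protocol 6.2.3.1 asks patients who stop drug early to attend the remaining treatment visits and FU1 and FU2, and to skip FU3.

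**The concern.** The retention rule means that readings long after the last dose are planned. The patients who produce them do not have the Week 56 visit, so the one capped vital-sign row in Part B does not touch them.

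Their later readings enter the by-visit changes, the potentially clinically important count and the maximum-QTc categories under the risankizumab columns. An any-value count or a maximum can change on one reading. By-visit means can be diluted by patients no longer exposed. Laboratory, adverse-event, vital-sign and ECG tables would then cover different risk periods for the same patients, and a reader of the tables could not see this.

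**Working it through.** **1. The limit.** 15 weeks × 7 = 105 days, so protocol and SAP agree. SAP 11.2.1 equates 105 days with 5 half-lives, that is 21 days each.

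**2. Inputs for Part B.** Rx Day 1 is the Week 16 dose or visit. Target dosing days are Rx Days 1, 85 and 169 (SAP Table 9). The limit is the last-dose day + 105:

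- last dose Week 16: 1 + 105 = Day 106
- last dose Week 28: 85 + 105 = Day 190
- last dose Week 40: 169 + 105 = Day 274

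**3. Days since last dose at each target day** (target day minus last-dose day; Tables 6 and 7):

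| Visit (Rx Day) | Last dose Week 16 | Last dose Week 28 | Vital-sign row | ECG row |
|---|---|---|---|---|
| Week 22 (43) | 42 | – | uncapped | none |
| Week 28 (85) | 84 | 0 | uncapped | uncapped |
| Week 34 (127) | **126** | 42 | uncapped | none |
| Week 40 (169) | **168** | 84 | uncapped | uncapped |
| Week 46 (211) | **210** | **126** | uncapped | none |
| Week 52 (253) | **252** | **168** | uncapped | capped |

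Bold figures exceed 105. After a last dose at Week 16, four vital-sign visits and one ECG visit (Week 40) are past the limit in uncapped rows. After a last dose at Week 28, two vital-sign visits are, and no ECG at its target day. In the SAP's half-lives, 168 days is 168/21 = 8 and 252 days is 252/21 = 12.

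**4. Off-target readings.** The Week 28 ECG row runs to Day 127, which is 127 − 106 = 21 days past the limit for a last dose at Week 16. The Week 40 row runs to Day 211, which is 211 − 190 = 21 days past it for a last dose at Week 28. A patient who leaves the trial after the Week 16 dose has FU3 vital signs 16 × 7 = 112 days later. That is Rx Day 113, inside the uncapped Week 34 row [107, 148].

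**5. Patients dosed through Week 40.** Week 52 is 253 − 169 = 84 days after the dose and is within the limit. Week 56 is 281 − 169 = 112 days and is removed from the by-visit table by note b. The any-value count is not tied to visit windows, so read literally it would still admit that Week 56 reading for patients who do not enter the extension.

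**6. Part A.** The earliest possible limit is 1 + 105 = Day 106. The uncapped rows end at Day 99 (vital signs) and Day 71 (ECG), and the Week 16 rows are capped. There is no gap.

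**7. Laboratory values against ECG.** They share the rows of Table 7. For a last dose at Week 16, the Week 40 laboratory values are dropped by 11.3, the Week 40 ECG is kept, and the Week 52 ECG is dropped by the footnote.

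**8. Size.** The documents give no rate of stopping drug while staying in the trial. There are 168 × 6 = 1008 scheduled vital-sign visits from Week 22 to Week 52. Suppose a given share stops after the Week 16 dose and attends every later visit:

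| Assumed share | Patients | Visits past 105 days | Of 1008 |
|---|---|---|---|
| 1% | about 2 | 2 × 4 = 8 | 0.8% |
| 5% | about 8 | 8 × 4 = 32 | 3.2% |
| 10% | about 17 | 17 × 4 = 68 | 6.7% |

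These are upper figures for each share, because a patient last dosed at Week 28 contributes two visits, not four. Each patient last dosed at Week 16 adds one scheduled ECG.

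**The case against.** Several limits on the point stand.

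- **Final values are protected.** SAP 11.4.2 refers to Section 6.0 for final values, and those definitions stop at 105 days. A reader might infer that vital signs have no limit outside the footnotes. That is not so.
- **The placebo comparison is untouched.** Protocol 3.2 says only adverse events in the first 16 weeks can be compared directly with placebo, and Part A has no gap for either measure. What remains is uncontrolled description.
- **The protocol is not contradicted.** A reader might infer a breach of the 15-week rule, but Protocol 5.3.6.2 concerns adverse events. Protocol 7.3.4 has vital signs assessed over the whole trial with no residual-effect limit.
- **ECG is not repeated in ALL_RZB.** SAP 11.5 confines ECG to the Safety Population. Of the outputs at issue, only the potentially clinically important vital-sign table is repeated.
- **Few patients may be involved.** Their number is unknown and may be small.

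One could add that a common risk window for all safety measures is a matter of preference. This does not explain the SAP as written. A plan to keep all off-drug readings would not cap the last row, and a plan to exclude them would not leave the earlier rows open. No reason is given for treating ECG and laboratory values from the same visit differently. If a longer period is intended for vital signs and ECG, the SAP should say so.

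**Conclusion.** The point holds as an inconsistency within the SAP, confined to Part B and to one ALL_RZB table. It affects the by-visit vital-sign and ECG summaries outside the two capped rows, the any-value vital-sign count and the maximum-QTc categories. It does not affect Part A, final-value summaries or efficacy, and it is not a departure from the protocol.

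Per patient, the effect is four vital-sign visits and one ECG (last dose Week 16) or two vital-sign visits (last dose Week 28), assuming visits and doses on their target days. Across the trial it is at most about 8 to 68 of 1008 vital-sign visits under the assumed 1% to 10%. No figure in that range should be read as an estimate. The importance is low and the correction is cheap.

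**What to change.** Add to SAP 11.4 and 11.5 the exclusion already in 11.3: values more than 105 days after the last dose of study drug are left out of the by-visit, potentially clinically important and maximum-QTc summaries. State that it applies to the ALL_RZB vital-sign table too. Keep later values in the listings.

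The footnotes of Tables 6 and 7 need not change. If they are extended to more rows, restrict them to safety analyses, as Table 2 note b does. The same rows also window PASI, sPGA, PSS, DLQI and joint counts, so an unqualified cap could remove early stoppers' later efficacy data from the ITT analysis.

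The cost is one sentence in each section and one filter in the programs. The downside is that a few off-drug readings leave the summary tables.
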